11.2.2 Analysis of Efficacy

The analysis of BP function endpoints and glycemic endpoints will be on an intention-to-treat basis. In cases where a treatment arm was not completed (and that arm was not repeated according to protocol criteria), available data from that arm will be used in the data analysis.

The Shapiro-Wilk test will be used to determine the normality of the residuals for each comparison. Summary tables that display descriptive statistics, including percentages, means or medians, and standard deviation and/or ranges, as appropriate, will be provided.

Clinical Trial Protocol
ZP4207-16051

Version number: 3.0
Amendment 2.0
Date: 03 August 2016

A paired t-test or the Wilcoxon signed rank test for comparison of means with normally or non-normally distributed residuals, respectively, will be used. In a secondary analysis, any period effect and any interaction between treatment and period will be looked for, although no such interaction is predicted for the efficacy outcome. Further details will be included in the SAP.

The number of patients and proportions of severe hypoglycemic events, symptomatic hypoglycemia, and carbohydrate interventions due to hypoglycemia with the event counts will be summarized descriptively, and the proportions will be analyzed by a Fisher's exact test if data allow.

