2.2 Secondary Objectives

The secondary objectives are to measure glycemic regulation, including hypoglycemia exposure (percent of time spent with CGM glucose < 60 mg/dL), evaluate BP device reliability, and to document the satisfaction of patients with the iLet with the goal of optimizing the functionality and user interface of the iLet.

[figure not shown]

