- Patients will exercise on a stationary bike with a heart rate from 120-140 beats per minute for a total of 4,000 heart beats (approximately 30 minutes). Patients will rate their exercise intensity using the Borg scale every 5 minutes, with the target intensity level between 12 and 14. Heart rate will be measured every 5 minutes.
- BG measurements will be obtained off of the IV line every 10 minutes. If BG is <80 mg/dL, BG measurements will be obtained off of the IV line every 5 minutes.
 - Carbohydrates will be given for any BG <50 mg/dL according to the following protocol: Dextrose (g) = BSA (m²)/[1.7 m² (women) or 1.9 m² (men)] *15 g.
 - Repeat treatments will be given at 15-minute intervals as long as BG remains <50 mg/dL.
- If there is an interruption in the Dexcom CGM output, trial staff will assist the patient in recovering CGM data streaming. If this requires replacement of the CGM sensor, BGs will be checked every 10 minutes (every 5 minutes if BG is <80 mg/dL) using blood from the IV until the CGM is able to be calibrated again. These BGs will be entered into the BP, which will treat them as CGM values and dose insulin and/or glucagon appropriately.
- If there is a complete failure of the BP operation, patients will take over their own BG control using their personal insulin pump until the BP can be brought back online. If BP control cannot be promptly resumed (e.g., within 30 minutes), the patient may be asked to repeat that trial day once.
- Patients may choose to withdraw from the trial at any time. If they withdraw from the trial, they should alert a provider immediately.
- Just prior to the end of the study visit, vital signs including body temperature and blood pressure will be obtained and a 12-lead ECG will be performed.
- After approximately Hour 8, but not earlier than at least 60 minutes after end of exercise, the BP will be stopped and the patient will continue with their personal insulin pump.

Clinical Trial Protocol
ZP4207-16051

Version number: 3.0
Amendment 2.0
Date: 03 August 2016

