7.4.4 Response to Hyperglycemia

- Trial staff will check the infusion site, BP, and insulin pump for normal operation any time BG is >300 mg/dL. If there is any suspicion of infusion set malfunction, the site should be replaced. Trial staff will check the BP for any malfunction and correct any problems that are found. If the BG remains >300 mg/dL for 2 hours despite troubleshooting, blood ketones will be measured. If the blood ketone result is >1.5 mmol/L, the visit will be stopped and rescheduled. The patient will be provided with insulin and a syringe to give an injection based on their correction factor.
- If a patient experiences diabetic ketoacidosis, his or her participation in the trial will be discontinued.
- If no correctable fault is found, but there is doubt regarding the correct function of the BP system, the treatment visit may be stopped and the visit rescheduled.

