 - >250 mg/dL
 - >300 mg/dL
- Number of severe hypoglycemic events (patients unable to self-treat, requiring the assistance of another person)
- Number of episodes of symptomatic hypoglycemia
- Number of carbohydrate interventions for hypoglycemia
- Total grams of carbohydrates taken for hypoglycemia
- Mean CGM glucose

Clinical Trial Protocol
ZP4207-16051

Version number: 3.0
Amendment 2.0
Date: 03 August 2016

8.2.3 **Non-glycemic**

- Glucagon/ZP4207 total delivery per kg of body mass
- Insulin total delivery per kg of body mass
- Number of unscheduled infusion set replacements
- Number of unscheduled CGM sensor changes

9 **LABORATORY ASSESSMENTS**

Descriptions of sample handling and sample processing, storage, and shipment at the site will be included in the laboratory manual.

The responsible laboratories are listed in the [address list](#).

9.1 **Safety Laboratory Assessments**

Chemistry and hematology samples will be collected at specified time points. See [Appendix A](#) for the schedule of procedures and [Appendix B](#) for a list of clinical laboratory analytes.

9.2 **Pharmacodynamic Assessments (Plasma Glucose)**

At Visit 3 and Visit 4, plasma glucose samples will be taken from the IV at least hourly in parallel with ZP4207/glucagon exposure sampling and measured using the YSI 2300 STAT Plus. If the YSI 2300 STAT Plus and/or IV fails, the Nova StatStrip Xpress will be used for glucose measurements. If BG is <150 mg/dL, then sampling will be every 30 minutes. If BG is <100 mg/dL, then sampling will be every 20 minutes. If BG is <80 mg/dL, then sampling will be every 10 minutes. The actual time of sampling will be recorded in the eCRF.

9.3 **Exposure Assessments (ZP4207 and Glucagon)**

At Visit 3 and Visit 4, ZP4207/glucagon exposure sampling will be collected at least hourly. If BG is <150 mg/dL, more frequent samples for plasma ZP4207/glucagon may be drawn at the discretion of the Investigator. The actual time of sampling will be recorded in the eCRF.

Bioanalytical Reports will be prepared.

9.4 **Anti-drug Antibody Assessments**

Blood samples (including back-up samples) for serum anti-ZP4207 and anti-glucagon antibodies will be taken at Visit 3 and the Follow-up Visit 6.

A Bioanalytical Report will be prepared.

10 **SAFETY REPORTING**

10.1 **Adverse Events**

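### Section 11.2.2 implies that a repeated visit replaces the failed attempt, so the percentage-based device-reliability and high-glucose endpoints can omit the worst attempts despite the intention-to-treat label

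*Protocol*

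**What the plan says.** All references are to the current protocol, version 3.0.

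- **Analysis principle (11.2.2):** "The analysis of BP function endpoints and glycemic endpoints will be on an intention-to-treat basis".
- **Incomplete arms (11.2.2):** where a "treatment arm was not completed (and that arm was not repeated according to protocol criteria), available data from that arm will be used". The section does not say what happens to the first attempt when the arm was repeated.
- **Complete BP failure (7.4.1):** "If BP control cannot be promptly resumed (e.g., within 30 minutes), the patient may be asked to repeat that trial day once".
- **Prolonged hyperglycemia (7.4.4):** "If the BG remains >300 mg/dL for 2 hours despite troubleshooting, blood ketones will be measured", and then "If the blood ketone result is >1.5 mmol/L, the visit will be stopped and rescheduled".
- **Doubt about the device, also in the hyperglycemia section (7.4.4):** where checks turn up nothing to correct and yet "there is doubt regarding the correct function of the BP system, the treatment visit may be stopped and the visit rescheduled".
- **Objective (2.2):** one secondary objective is to "evaluate BP device reliability".
- **Endpoints (8.2.1 and 8.2.2):** the quantitative reliability measures are average percentages, such as the share of calculated doses delivered and the share of 5-minute steps in which the device works normally. The glycemic endpoints include mean CGM glucose and the fractions of time above 250 and above 300 mg/dL.

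**The concern.** Under an intention-to-treat approach, a visit that was started counts as it turned out. The parenthesis in 11.2.2 points the other way: data from an incomplete arm are used on condition that the arm was not repeated. The events that lead to a repeat are not incidental to the endpoints. A complete, unresolved BP failure is the worst result a reliability percentage can record. Two hours above 300 mg/dL with raised ketones is among the worst results for mean glucose and time in the high ranges. If the repeat stands in for such an attempt, the summary describes the device after its bad days have been replayed.

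Two of the three decisions are left to judgment, and staff know which product is in the pump. Replacement could therefore differ between products without anyone intending it. Section 1.1 says the results will guide the next-generation device and larger outpatient trials, so an optimistic reliability percentage would carry forward.

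**Working it through.** The protocol gives no failure rate, reliability target or sample-size calculation (11.2.4), so there is no figure of its own to reproduce. The check has two parts: reading the repeat rules against the analysis rule, and sizing the effect under stated assumptions.

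**1. What leads to a second attempt**

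| Event | Section | Decision | Limit on repeats | Endpoints exposed |
|---|---|---|---|---|
| Complete BP failure, not promptly resumed | 7.4.1 | discretionary | once | BP-function percentages; all CGM endpoints of that visit |
| Doubt about BP function during hyperglycemia | 7.4.4 | discretionary | none stated | BP-function percentages; mean glucose, time >250 and >300 mg/dL |
| BG >300 mg/dL for 2 h, then ketones >1.5 mmol/L | 7.4.4 | mandatory | none stated | mean glucose, time >250 and >300 mg/dL |
| Hypoglycemia with doubt about BP function | 7.4.3 | backup system may be started | no repeat | stays in the visit |

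**2. Steps per visit.** The BP runs for about 8 h (7.4.1): 8 × 12 = 96 five-minute steps. A 30-minute outage is 6 steps, and 6/96 = 6.25%. If every longer outage led to a repeat, a single complete failure could cost a retained visit no more than about 6 steps.

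**3. Effect on an arm mean of normal-step percentage.** Let n be the visits in the arm, k the failed visits, f the fraction of the visit completed before failure, and M the share of normal steps while the device is running. Steps after the failure count as not functioning, and a repeat is assumed to run at M.

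- First attempt kept: [(n − k)M + k·f·M]/n
- Repeat only: M
- Difference: k·M·(1 − f)/n

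Assume M = 0.98. Section 11.2.4 expects 10 to 12 randomized patients, hence n = 10 or 12 visits per arm.

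| n | k | f = 0.75 | f = 0.50 | f = 0.25 |
|---|---|---|---|---|
| 10 | 1 | 2.45 points | 4.90 | 7.35 |
| 12 | 1 | 2.04 | 4.08 | 6.13 |
| 10 | 2 | 4.90 | 9.80 | 14.70 |

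For one failure halfway through, the arm mean is 98.0 − 4.9 = 93.1% (n = 10) or 98.0 − 4.1 = 93.9% (n = 12) with the first attempt kept. With the repeat alone it is 98.0%.

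**4. Effect on time >300 mg/dL.** Two hours is 24 readings. If the visit stops at Hour 4 and is analysed up to the stop, 24/48 = 50% of its readings are in that range, which adds 50/10 = 5.0 points to a 10-visit arm mean. A stop at Hour 3 gives 24/36 = 66.7%, or 6.7 points. If a repeat with no such readings replaces the attempt, the contribution is zero. This assumes CGM tracks the BG trigger and that the other visits have no time >300 mg/dL.

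**5. How likely a failed visit is.** With 2 × 10 = 20 visits and an assumed failure rate p per visit, the chance of at least one failure is 1 − (1 − p)^20: 33% at p = 2%, 64% at 5% and 88% at 10%. With 24 visits the figures are 38%, 71% and 92%. The rates are assumptions. Only failures followed by a repeat affect the result.

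**The case against.** The strongest reply is that 11.2.2 says only what happens when an arm was not repeated. It never states that a failed attempt is dropped, and it defers details to the SAP. That is fair as far as it goes: exclusion is implied, not written. But the parenthesis makes use of the data conditional on there being no repeat, and no other passage brings the first attempt back.

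A reader might infer that repeated failures vanish from the trial altogether. The documents do not support that. The technical-fault list is itself a BP-function endpoint (8.2.1), time off BP control is collected (7.4.2), device deficiencies must be documented and reported (10.3), and adverse events are analysed in the Safety Analysis Set (11.1). Outages resolved promptly and failures not repeated also stay in. Only the percentage and CGM summaries are exposed.

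Time <60 mg/dL, the one glycemic measure named in the secondary objective, is little affected. Once the BP has started, hypoglycemia does not trigger a repeat; doubt about the device then leads to a backup system (7.4.3). Section 7.4.4 also speaks of rescheduling rather than repeating, so treating its stops as repeats under protocol criteria is itself a reading, though a natural one.

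The size depends on the scoring of steps after a failure. The protocol fixes no denominator. If only the steps before the failure were scored, an attempt that was normal until it failed would look nearly perfect even when retained. This objection stands, and the fix has to settle the denominator as well as the choice of attempt.

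Finally, this is a feasibility trial with a primary safety endpoint (8.1), which the rule does not touch. That lowers the priority of the point but does not remove it.

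**Conclusion.** The point holds in limited form. As naturally read, 11.2.2 conflicts with its own intention-to-treat statement and moves the BP-function percentages, mean glucose and time >250 and >300 mg/dL in the favourable direction whenever a failed visit is repeated. For one repeated failure among 10 visits, the illustrative shift in the normal-step percentage is about 2.4 to 7.4 points. This rests on assumed 98% functioning elsewhere and on counting steps after the failure as not functioning. The actual shift could be zero if no visit is repeated.

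A reader might go further and infer that incomplete visits kept in the analysis flatter the worse-tolerated product, because totals such as drug delivered or carbohydrate taken accrue over fewer hours. Nothing in the documents shows that incomplete visits would differ by product, and adjusting totals for exposure is ordinary SAP content. That is not part of this finding.

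The rule should be fixed because it bears on a stated secondary objective and the remedy is cheap. It does not undermine the trial's primary safety assessment.

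**What to change.** Amend 11.2.2, and carry the same rule into the SAP, so that it states:

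1. For the BP-function endpoints, the first attempt at every started visit is primary. Planned steps after a device failure count as not functioning. A first attempt stopped for a non-device reason is analysed up to the stop. The analysis using the repeat is shown as a sensitivity analysis.
2. Glycemic endpoints are reported both ways, with the first attempt up to the stop and with the repeat, each clearly labelled.
3. The number of repeated or rescheduled visits is tabulated by treatment and reason.

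Sections 7.4.1 and 7.4.4 also need to be reconciled, since one allows a single repeat and the other states no limit on rescheduling. Section 11.2.2 should then say which of these events it means by its protocol criteria for a repeat.

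The cost is a few sentences. The device logs and time off BP control are already collected, and the analysis changes alter no clinical rule. The one real downside is that reported reliability may be less favourable. The wording should be settled before outcomes are examined, because the trial is open-label and some repeats are discretionary.

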The BU Investigators have recently designed, built, and tested a proprietary first-generation of such a fully integrated BP system, referred to as the iLet and the iLet infusion set. The iLet is a dual-chamber infusion system that currently incorporates the Dexcom G4 CGM technology, a custom user interface with touchscreen display, and all of the mathematical dosing algorithms that were tested in and validated using the iPhone-based BP in outpatient studies over the past 3 years. The iLet infusion set provides 2 independent subcutaneous (SC) fluid pathways from the iLet to the patient (1 for insulin and the other for glucagon). One tube connects to the prefilled insulin cartridge and the other tube connects to the fillable (single-use) glucagon cartridge.

In order to provide automatic BG regulation, the iLet has the ability to deliver both insulin and glucagon. However, currently available glucagon formulations have limited stability at room temperature, necessitating frequent changes to the glucagon infusion set. Therefore, the current trial is designed to test the glucagon analog ZP4207 in the iLet, as this peptide analog of human glucagon is provided in a liquid formulation stable at room temperature.

Clinical Trial Protocol
ZP4207-16051

Version number: 3.0
Amendment 2.0
Date: 03 August 2016

The current trial is a first feasibility trial designed to use the first-generation iLet and iLet infusion set to compare ZP4207 with marketed glucagon (Lilly). The trial is intended to demonstrate the safety and tolerability of ZP4207 in the iLet and the feasibility of achieving comparable autonomous glycemic control. It is not intended to comprehensively demonstrate the definitive efficacy of the iLet in extended, continuous daily use, but rather to demonstrate its functionality and accuracy in a practical, albeit very controlled, clinical setting. The trial is expected to provide practical information that will benefit the design of a next-generation iLet and iLet infusion set and help pave the way for a more comprehensive outpatient home-use Phase 2 trial and ultimately a pivotal trial where comprehensive safety and efficacy through continuous full daily use of the iLet with ZP4207 will be documented.

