5 ASSIGNMENT TO TREATMENT GROUPS

This trial is an open-label, randomized cross-over trial. Patients who have completed the Screening Visit and meet all of the inclusion and none of exclusion criteria will be enrolled into the trial. All patients will participate in two 1-day treatment arms in random order (iLet using ZP4207 and iLet using Lilly glucagon) according to a pre-generated randomization scheme. Up to 2 patients may participate in the trial per day. The order of the iLet visits will be randomized in blocks of 2 patients.

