11 STATISTICS

11.1 Analysis Populations

The following analysis sets are defined in accordance with the ICH-E9 guidance:

The Full Analysis Set is based on the intention-to-treat principle and includes all randomized patients. In exceptional cases, patients from the Full Analysis Set may be excluded (will be decided in the database review [DBR] meeting). In such cases, the exclusion will be justified and documented. Patients will contribute to the evaluation "as randomized."

The Per-Protocol Set includes all patients of the Full Analysis Set who completed the trial without any major protocol violations. Patients in the Per-Protocol Set will contribute to the evaluation "as treated." This analysis will only be used if it is different than the Full Analysis Set.

The Safety Analysis Set includes all patients receiving at least 1 dose of the IMP. Patients in the Safety Analysis Set will contribute to the evaluation "as treated."

Analyses of efficacy endpoints will be based on the Full Analysis Set (and the Per-Protocol Set if necessary). This decision will be made in the DBR meeting. The analysis of the safety endpoints will be based on the Safety Analysis Set.

Before data are released for statistical analysis, a blinded review of all data will take place to identify protocol deviations that may potentially affect the results. At this time, it will be determined if patients and/or data should be excluded from the analysis. Furthermore, outliers will be identified by data review according to ICH-E9.

Obviously erroneous data points may be excluded from the analyses or re-analyzed (e.g., serum concentrations). The decision to re-analyze or exclude data points from the statistical analysis is the joint responsibility of the Sponsor, the Principal Investigator, and the Trial Statistician.

The patients or observations to be excluded and the reason for their exclusion will be documented and signed by those responsible prior to database release. The documentation will be stored together with the remaining trial documentation. The patients and observations excluded from analysis sets, and the reason for this, will be described in the clinical trial report.

Clinical Trial Protocol
ZP4207-16051

Version number: 3.0
Amendment 2.0
Date: 03 August 2016

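### The main efficacy test leaves period unadjusted in a two-period cross-over, drops patients with no data in one arm, and is paired with an interaction check that cannot reassure

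*Protocol*

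**What the plan says.** Protocol section 5 describes a two-treatment, two-period cross-over: "All patients will participate in two 1-day treatment arms in random order (iLet using ZP4207 and iLet using Lilly glucagon"), and "The order of the iLet visits will be randomized in blocks of 2 patients". There are therefore two sequences, AB and BA, balanced at randomisation to within one patient.

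For efficacy, section 11.2.2 states: "A paired t-test or the Wilcoxon signed rank test for comparison of means with normally or non-normally distributed residuals, respectively, will be used". Period comes next, but only as a follow-up: "In a secondary analysis, any period effect and any interaction between treatment and period will be looked for". The protocol adds that no such interaction is predicted and that the SAP will give further details.

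On who is analysed, section 11.1 states: "The Full Analysis Set is based on the intention-to-treat principle and includes all randomized patients". Section 11.2.2 adds: "The analysis of BP function endpoints and glycemic endpoints will be on an intention-to-treat basis". If an arm was not completed and not repeated, "available data from that arm will be used in the data analysis".

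On size, section 11.2.4 expects 10 to 12 randomised patients with no formal calculation. Section 3.3 expects up to 10 completers and foresees some discontinuations.

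**The concern.** The design randomises order, yet the main test does not use it. In a paired analysis, any difference between first and second visit goes into the spread of the within-patient differences. If the two sequences end up unequal, part of it also goes into the treatment estimate.

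A paired difference needs a value from both visits. A randomised patient with nothing recorded in one arm cannot enter the test, although the stated set is all randomised patients.

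The planned treatment-by-period test looks like a safeguard. In an AB/BA design it is the same contrast as sequence and cannot be separated from carry-over. It is also tested between patients, with five or six per sequence.

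At stake are wider intervals than necessary, some bias if dropout is uneven, and a null interaction test being taken as evidence against carry-over.

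**Working it through.** The protocol gives no SD, effect size or power for efficacy, so there is no planned figure to reproduce. The sizes of period shift, carry-over and correlation below are assumptions. N = 10 is from section 3.3, and five or six per sequence follows from sections 5 and 11.2.4.

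**Precision, balanced sequences (5 + 5).** Let the SD of the within-patient difference (A minus B) be 1 and the period difference be k. Sequence AB has mean τ − k and BA has τ + k.
- The paired test's expected variance is inflated by 1 + k²·N/(N−1).
- Its 95% half-width, using the root of that expected variance, is 2.262/√10 × √(1 + k²·10/9).
- The period-adjusted half-width (mean of the two within-sequence means, 8 df) is 2.306/√10 = 0.729, whatever k is.

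| k (SD) | Paired | Adjusted | Ratio |
|---|---|---|---|
| 0 | 0.715 | 0.729 | 0.98 |
| 0.25 | 0.740 | 0.729 | 1.01 |
| 0.5 | 0.809 | 0.729 | 1.11 |
| 0.75 | 0.912 | 0.729 | 1.25 |

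The two are equal at k ≈ 0.19 SD, where 1 + k²·10/9 = (2.306/2.262)².

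**Error rates.** Simulation (40,000 replicates, two-sided 5%, 5 + 5) gave the paired test a type I error of 0.048, 0.030 and 0.007 at k = 0, 0.5 and 1. Its power for a 1-SD effect was 0.80, 0.72 and 0.48. The adjusted analysis kept about 0.05 and 0.79 throughout. So the paired test is conservative, not invalid.

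**Bias, unequal sequences.** The expected paired mean is τ + ((n_BA − n_AB)/n)·k. With 6 AB and 4 BA this is τ − 0.2k, a bias of 0.10 SD at k = 0.5 and 0.20 SD at k = 1. The sign depends on which sequence loses patients. The adjusted estimate is unbiased. Its half-width is 2.306 × √((1/6 + 1/4)/4) = 0.744.

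**Lost patients.** If 1, 2 or 3 of 12 have data from one arm only, the test uses 11, 10 or 9 pairs. With 10 complete patients and 2 single-visit patients, a mixed model using all visits lowers the standard error by about 1–4% (within-patient correlation 0.7 down to 0.3).

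**The interaction check.** Order the four cells as AB period 1, AB period 2, BA period 1, BA period 2, with ±1 coding:
- treatment (1, −1, −1, 1)
- period (−1, 1, −1, 1)
- treatment × period (−1, −1, 1, 1), exactly minus the sequence column (1, 1, −1, −1)
- carry-over (0, 1, 0, −1) = −0.5 × treatment − 0.5 × (treatment × period)

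Four cell means support four parameters, so adding carry-over leaves the rank at 4.

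The test compares patient totals between sequences. For differential carry-over λ, in single-visit SDs, and correlation ρ, the noncentrality is λ/(√(2+2ρ)·√(2/n)) on 2n − 2 df. With λ = 1, ρ = 0.5 and n = 5 it is 1/(1.732 × 0.632) = 0.913, and power is 13%. Over ρ = 0.3–0.7 and n = 5–6, power is 12–16% for λ = 1 and 7–8% for λ = 0.5. Such carry-over would bias the treatment estimate by λ/2, that is 0.5 and 0.25 SD.

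**The case against.** Period is not ignored: the protocol plans to look for it and defers detail to the SAP, which is not shown. That stands. The point is only that the stated main comparison is not adjusted.

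Blocks of 2 keep the sequences balanced, so without uneven dropout there is no bias. That also stands. At a 0.5-SD shift, even the 6 versus 4 bias is 0.1 SD against a half-width above 0.7 SD.

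The design also restrains period effects. There is a training visit (7.3), and section 7.4.1 requires weight-only initialisation of the algorithm, the same meal at the same time on both visits, and exercise of a fixed number of heart beats. A shift may be small, and below about 0.19 SD the paired interval is slightly narrower.

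The intention-to-treat conflict is narrow. A visit begun but not finished still gives a value under the available-data rule, and some visits may be rescheduled or repeated.

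A reader might go further and infer that a non-significant result will be presented as comparability, since section 1.1 speaks of "the feasibility of achieving comparable autonomous glycemic control". The documents do not support this. That wording concerns feasibility, the same section disclaims definitive efficacy, section 2.2 speaks of measuring glycemic regulation, and nothing says how p > 0.05 will be read.

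Nor can the loss be put in mg/dL from the studies in Figure 1. Those compare the bionic pancreas with usual care over at least 5 days. This trial compares two glucagons in the same device and algorithm over about 8 hours.

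**Conclusion.** The point holds as a modest improvement. The protocol itself names an unadjusted paired test as the main efficacy comparison in an AB/BA cross-over. If a period effect exists, the cost is precision: about 1%, 11% and 25% in CI width at assumed shifts of 0.25, 0.5 and 0.75 SD with 10 balanced completers. Bias arises only if a period effect and unequal sequences occur together. The loss of randomised patients is real but limited to those with no data in one arm.

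The aliasing of the interaction test is a property of the design and rests on no assumption. Its 12–16% power assumes a 1-SD carry-over and correlations of 0.3–0.7. A null result must not be used as reassurance, even though the washout of at least 24 hours and the re-initialised algorithm may well keep carry-over small.

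The primary endpoint is safety, efficacy is secondary, and the trial is a first feasibility study without formal power. Nothing here threatens its main purpose.

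**What to change.** In section 11.2.2, and in the SAP to match:
- Make the main efficacy analysis a linear mixed model with treatment and period as fixed effects and patient as random effect, using every available visit. Leave sequence out of the fixed effects, because it is the same aliased contrast as the interaction.
- Report the treatment difference with its 95% CI as the result.
- Where a rank method is needed, compare within-patient period differences between the two sequences with a rank-sum test.
- Drop the treatment-by-period test, or state that it does not inform the choice or reading of the main analysis.

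The cost is a change of wording and one degree of freedom. With balanced sequences and no period effect, the CI is about 2% wider (0.729 against 0.715). At 6 versus 4 it is about 4% wider (0.744 against 0.715). No further patients or data are needed.
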